15.14.2 Headache End Date and Time

If the end date and time for a headache recorded in the eDiary is missing, the headache end date and time will be imputed as follows:

- If there exists an entry in the evening eDiary at a date after the date of the start of the headache entered in the headache eDiary, the headache end date and time is imputed with the date and time of the last evening eDiary entry.
- If there are no entries in the evening eDiary after the date of the start of the headache entered in the headache eDiary, the headache end date and time is imputed with the start date of the headache and the time 23:59.

Note that for each participant, it is only possible to have a missing end date and time for the last headache ever entered, since a participant needs to complete a headache in order to report a new one in the headache eDiary.

15.14.3 Adverse Event Start and Stop Dates

Imputation of partially or completely missing dates will be included in data in order to document the classification of the treatment emergent status. For an adverse event with an imputed start date, the classification of treatment emergent will depend only on whether the imputed date is the same as the date(s) of infusion and not the timepoint of the infusion, since start times for adverse events will not be imputed. No duration will be calculated for adverse events with incomplete start-or-stop dates or for ongoing adverse events.

Imputation will follow the algorithm below. If an imputed start date after this procedure is after the end date, the start date will be set to the end date.

Start Dates

Participants with no IMP infusion

For participants who have not been treated, the imputation of AE start date will be performed as follows, where UK and UKN indicate unknown or missing day and month, respectively:

- UK-MMM-YYYY: The start date will be imputed with either the 1st of the month, or date of Visit 1. Date of Visit 1 will be used if that is the later of the two and if it is within the specified month and year
- UK-UKN-YYYY: The start date will be imputed with either JAN 1, or date of Visit 1. Date of Visit 1 will be used if it is within the specified year

If the AE start date is completely missing, it will be set equal to the date of Visit 1.

Patients who received IMP infusion

For participants, who have been treated, the imputation of AE start dates will be performed as follows:

- **UK-MMM-YYYY:**
 - If the year and month are equal to the year and month of treatment start date, the adverse event start date is imputed with the date of IMP dose
 - If the year is equal to the year of treatment start date: If the month is prior to the treatment start date, the adverse event start date is imputed with the last day of the month. If the month is equal to the month of the treatment start date, see above. If the month is after the month of the treatment start date, the adverse event start date is imputed with the first day of the month
 - If the year is prior to treatment start date, the adverse event start date is imputed with the last day of the month
 - If the year is after the year of treatment start date, the adverse event start date is imputed with the first day of the month
- **UK-UKN-YYYY:**
 - If the year is equal to the year of treatment start date, the adverse event start date is imputed with treatment start date
 - If the year is prior to the year of treatment start date, the adverse event start date is imputed with 31-DEC-YYYY
 - If the year is after the year of treatment start date, the adverse event start date is imputed with 01-JAN-YYYY

If the AE start date is completely missing, it will be set equal to treatment start date.

End Dates

Missing AE end dates will not be imputed.

Incomplete Intensity Change Dates

If the day is missing in a date of intensity change for an adverse event, the date will be imputed using the same algorithm as described above for incomplete adverse event start dates.

If this results in an imputed start date that is after the end date of the original event or after an intensity change that comes after the intensity change in question, the start date will be imputed with the end date of the original event or the date of the later intensity or change.

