12.1.2 Classification of Adverse Events

Adverse events will be classified according to the time of onset of the adverse event:

pre-treatment adverse event – an adverse event that starts on or after the date the participant signed the *Informed Consent Form* and prior to the date and time of first dose of IMP

treatment-emergent adverse event (TEAE) – an adverse event that starts during or after administration of the first dose of IMP, or a pre-treatment adverse event that increases in intensity or becomes serious during or after administration of the first dose of IMP

For handling of adverse events with incomplete start dates to facilitate this classification, see Section 15.14.3. Note that adverse events with incomplete start dates will be classified as treatment-emergent simply if the imputed start date is on or after the date of first IMP infusion, since the start time of the adverse event will not be imputed, unless the investigator in such a case has assessed that the causality to IMP is “Not Related - Prior to IMP”.

An adverse event is considered causally related to the use of the IMP when the causality assessment by the investigator is probable or possible. If the causality assessment is missing, the adverse event is considered causally related.

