12.1.3 Allocation of TEAEs to Treatment Periods

TEAEs will be allocated to treatment periods according to the time of onset of the adverse event:

- *TEAE in the Placebo-controlled Period* – a TEAE that starts before the date and time of the start of Visit 5 IMP infusion, or, for the participants with no Visit 5 IMP infusion, a TEAE that starts before Week 12.
- *TEAE in the Open-label Period* – a TEAE that starts, increases in intensity or becomes serious during or after administration of Visit 5 IMP infusion.

This implies that for participants in the APTS-FU, adverse events reported after withdrawal in the Placebo-controlled Period but before Week 12, will be allocated to the Placebo-controlled Period.

For allocation of TEAEs to treatment periods, the same rule for imputed dates as specified in Section 15.14.3 applies, i.e. for incomplete start dates, only the imputed start date and not the time (which will not be imputed) of the adverse event will be taken into account in the allocation of the TEAE to periods.

If an adverse event starts on the day of the Visit 5 IMP infusion, but with an unknown start time, the adverse event will be classified as treatment-emergent in the Placebo-controlled Period.

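### Partial adverse-event start dates are imputed against the first infusion only, so open-label onsets with an unknown day in the Visit 5 month, and most known only by year, are counted in the Placebo-controlled Period

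*SAP*

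**What the plan says.** SAP 12.1.3 assigns a treatment-emergent adverse event (TEAE) to the Placebo-controlled Period if it is "a TEAE that starts before the date and time of the start of Visit 5 IMP infusion", and to the Open-label Period if it is "a TEAE that starts, increases in intensity or becomes serious during or after administration of Visit 5 IMP infusion". For incomplete dates it adds: "For allocation of TEAEs to treatment periods, the same rule for imputed dates as specified in Section 15.14.3 applies". Only the imputed date counts, because times are not imputed. The tie is settled explicitly: "If an adverse event starts on the day of the Visit 5 IMP infusion, but with an unknown start time", the event goes to the Placebo-controlled Period.

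SAP 15.14.3 then compares the partial date with one anchor, the treatment start date:

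- Unknown day, same year as treatment start: if the recorded "month is after the month of the treatment start date, the adverse event start date is imputed with the first day of the month". An unknown day in a later year also becomes the 1st of the recorded month.
- Unknown month: "If the year is equal to the year of treatment start date, the adverse event start date is imputed with treatment start date". A later year becomes 1 January of that year.
- Completely missing: the treatment start date.

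Incomplete intensity-change dates follow the same algorithm. The SAP does not formally define the treatment start date, but 12.1.2 supports reading it as the first infusion: an event with an incomplete date is "classified as treatment-emergent simply if the imputed start date is on or after the date of first IMP infusion". The introduction to 15.14.3 mentions infusion dates in a form that allows for more than one, but no branch of the algorithm uses Visit 5.

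**The concern.** The algorithm answers one question, whether an event began before or after first dosing, and its result is used for another, whether it began before or after Visit 5. At the first infusion an ambiguous date in the dosing month is set to the dosing date, so the event is attributed to treatment. At Visit 5, which is the first eptinezumab dose for placebo participants, an ambiguous date is pulled back to the period before the dose.

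The Placebo-controlled Period is the only randomised safety comparison. An open-label event that is pulled back is added to that comparison and leaves the open-label tables by treatment sequence, unless a later worsening, itself correctly dated, also qualifies it there. Year-only dates in the first-dosing year and missing dates are set to the first-infusion day itself. That bears on the day-of-dosing table in SAP 12.1.5 and the infusion-timed criteria for adverse events of special interest (AESI) in SAP 17.3.

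**Working it through.** The plan states no figure on this point, so the check applies the rules literally and counts.

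**Inputs from the documents.** The boundary is the start of the Visit 5 infusion (SAP 12.1.3). Visit 5 is 12 weeks after baseline, Day 84, with a window of ±2 days (Protocol 8.1 and Panel 2), so Day 82 to 86. The Open-label Period runs to Week 32, Day 224 (SAP 3.2). Imputation follows SAP 15.14.3 and the tie rule follows 12.1.3.

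**Assumptions (mine).** First infusions fall on each of the 365 days of 2023. True open-label onsets fall evenly on the days after Visit 5. With Visit 5 on Day 84 this gives 365 × (224 − 84) = 51,100 onsets.

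**Unknown day.** Visit 5 is at least 82 days after the first infusion, so the two are never in the same month. A date in the Visit 5 month is therefore always set to the 1st, which is on or before Visit 5.

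- Onsets in the Visit 5 month: 5,395, of which 5,395 (100%) go to the Placebo-controlled Period.
- Of these, 354 are ties. Visit 5 falls on the 1st for 12 start dates (April 2023 to March 2024, 366 days), and 366 − 12 = 354 days follow in those months. The unknown-time rule sends these to the Placebo-controlled Period too.
- Onsets in later months: 45,705, none misallocated.
- Share of all day-unknown open-label onsets: 5,395 / 51,100 = 10.6%.

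**Unknown month.**

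| Recorded year | Imputed date | Onsets | Misallocated |
|---|---|---|---|
| First-infusion year | First infusion | 29,470 | 100% |
| Later year, Visit 5 also in that year | 1 January | 11,760 | 100% |
| Later year, Visit 5 in first-infusion year | 1 January | 9,870 | 0% |

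The overall share is (29,470 + 11,760) / 51,100 = 80.7%. It is 80.4% with Visit 5 on Day 82 and 81.0% on Day 86. Counting onsets only to Week 24 gives 27,090 / 30,660 = 88.4%.

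**Missing start date.** Set to the first infusion, so always Placebo-controlled.

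**Examples.**

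- First infusion 20 June 2023, Visit 5 on 12 September, true onset 25 September. With the day unknown, the date becomes 1 September; with only the year known, 20 June. Both are Placebo-controlled.
- First infusion 10 August 2023, Visit 5 on 2 November, only the year 2024 recorded. The date becomes 1 January 2024, correctly Open-label.

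**Direction.** For an onset after first dosing, every imputed date is on or before the true onset, and the end-date safeguard in 15.14.3 can only move it earlier. The misallocation between periods runs one way.

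**The simple alternative.** Suppose every date that could fit an onset on or after Visit 5 were set to Visit 5 and called Open-label. Take true placebo-controlled onsets on Days 0 to 83: 365 × 84 = 30,660. Before any exemption based on other records, this would wrongly move 5,377 / 30,660 = 17.5% of day-unknown onsets and 27,090 / 30,660 = 88.4% of year-only onsets. Within the Visit 5 month it exchanges 5,395 errors for 5,377.

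**The case against.** The other side has several fair points.

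- Exposure is limited. Protocol 10.4 asks for start and stop dates. Adverse events are checked before, during and after the Visit 5 infusion (Protocol 8.5), and the next contact is at Week 16. Year-only onsets, to which the 81% applies, should be rare.
- No event loses treatment-emergent status. Documenting that status is the purpose 15.14.3 gives for the imputation, and an anchor at first dosing serves it.
- The problem is visible. The listings in SAP 12.1.1 show dates as collected, and the summaries are counts and percentages with no planned test.

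All of this stands and keeps the point modest. It does not change the fact that a stated rule assigns events to the wrong period.

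A reader might infer more than the documents support:

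- That every year-only open-label event is misplaced. About 19% (9,870 / 51,100) are placed correctly.
- That only the placebo column gains events. All participants who enter the Open-label Period receive eptinezumab at Visit 5 (Protocol 6.1), so both columns can gain, and the net effect on the between-arm difference cannot be derived.
- That sending every ambiguous event to Open-label would simply be cautious. The last check above shows it largely reverses the error, and in the eptinezumab arm it would remove true events from the randomised comparison.

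**Conclusion.** The point holds in this form and is worth correcting. All open-label onsets with an unknown day in the Visit 5 month, and all with no start date, go to the Placebo-controlled Period. Year-only onsets go there when the recorded year is the first-infusion year or contains Visit 5, about 81% to Week 32, but not when Visit 5 fell in the first-infusion year and a later year is recorded.

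The result for the Visit 5 month follows from the rules alone. The 10.6% and 81% rest on evenly spread start and onset dates. All figures read the treatment start date as the first infusion.

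These are shares of partially dated events, not of all adverse events. The documents give no count of partial dates; it is probably small, so the effect on the safety tables cannot be sized. Efficacy is untouched. The SAP also does not say how an event first reported after the Placebo-controlled database is locked (Section 4), but imputed back into that period, would be tabulated.

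**What to change.** Amend SAP 15.14.3 and 12.1.3 for participants with a Visit 5 infusion whose partial or missing start date is compatible with onset both before and after Visit 5:

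- Allocate to the Placebo-controlled Period if the event was recorded at or before the Visit 5 pre-infusion adverse-event check, or if its end date is before Visit 5.
- Otherwise allocate to the Open-label Period, with the imputed start date no earlier than the Visit 5 date.
- State that this overrides the unknown-time sentence in 12.1.3 for imputed dates. Without that, an event imputed to the Visit 5 date would return to the Placebo-controlled Period.
- State that an event with an imputed day does not enter the day-of-dosing summary or the infusion-window AESI summaries solely because of the imputation.
- Apply the same rule to incomplete intensity-change dates. SAP 15.14.4 borrows the start-date algorithm for medications, so say whether the change extends there.

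The Protocol already requires the pre-infusion check (8.5 and Panel 2), so the rule needs no new data collection. The cost is a few lines of SAP text and programming. The downside is that a few events that began before Visit 5 but were first reported afterwards will move to the Open-label Period, in both arms. Listing the affected events under both allocations would show how much this matters.

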15.14.4 Medication Start and Stop Dates

Imputation of incomplete or partially missing dates will be performed in order to document the assigned categories specified in Section 8.

The algorithm for imputing the start dates will follow the one used for imputing adverse event start dates, see Section 15.14.3.

For imputing stop dates, the following will apply, where UK and UKN indicate unknown or missing day and month, respectively:

- **UK-MMM-YYYY:** Medication end date is imputed with the last day of the month

- UK-UKN-YYYY: Medication end date is imputed with 31-DEC-YYYY

Medications marked as ongoing are considered concomitant medications in one or both of the periods (Placebo-controlled Period and Open-label Period), depending on the (possibly imputed) start date, i.e. if the start date is at or after the date of Visit 5 IMP infusion, the medication is only considered ongoing in the Open-label Period.

15.15 Pooling Rule for the Country Variable for the Logistic Regression Models

In case of convergence, sparsity or separation issues, Firth's penalized likelihood method will be used. If it still fails to converge after Firth's penalized likelihood method applied, pooled country strategy will be used for analysis. Only a country with at least 5 participants is included as a standalone country. To avoid loss of information, small countries will be pooled from largest to smallest until there are 5 participants in the pooled country.

16 References

- 1 International Headache Society (IHS), Headache Classification Committee. The International Classification of Headache Disorders, 3rd edition 2018 (ICHD-3 2018).
- 2 Little R and Yau L. Intent-to-treat analysis for longitudinal studies with drop-outs. *Biometrics*. 1996; 52: 1324-1333.
- 8 Mapi Research Trust. Migraine specific quality of life questionnaire. Version 2.1. Scaling and scoring. Version 1.0. November 2017.

17.1 Schedule of Trial Procedures

Table 13 Trial Procedures and Assessments

Visit Name	Screening	Placebo-controlled Period			Open-label Period			Safety Follow-up Decentralized ^c	Withdrawal ^d
		Baseline + IMP	PO Visit, Decentralized ^c	Decentralized ^c	IMP	Decentralized ^c	EoT Visit		
Visit Number	1	2	3	4	5	6	7	8	WD
End of Week ^a	-4	0	4	8	12	16	24	32	
Visit Window ^b (days relative to nominal visit)	-2		±2	±2	±2	±2	±2	±5	
Screening and Baseline Procedures and Assessments									
Signed informed consent (including digital wearables)	√								
Demographics (age, sex, and race)	√								
Diagnosis (migraine and MOH)	√								
Disease-specific history ^c	√								
Relevant history (social, medical, psychiatric, neurological)	√								
Previous migraine and preventive medication use ^c including treatment failures	√								
Recent medication (prescription and non-prescription: traditional herbal medicines, non-pharmacological interventions, vitamins and mineral supplements)	√								
Height and weight	√								
Examinations (physical, neurological)	√								
Blood sampling for eligibility (including serology and other screening, for example β -HCG and FSH)	√								
Urine drug and alcohol screen	√								
ECG	√								
C-SSRS ^f	√								
Inclusion/exclusion criteria	√	√							
Signs and symptoms present at Screening and/or Baseline (before IMP intake) (recorded on an Adverse Event Form)	√	√							
Randomization			√						

Visit Name	Screening	Placebo-controlled Period			Open-label Period			Safety Follow-up Decentralized	Withdrawal
		Baseline + IMP	PO Visit, Decentralized ^c	Decentralized ^c	IMP	Decentralized ^c	EoT Visit		
Visit Number	1	2	3	4	5	6	7	8	W D
End of Week ^a	-4	0	4	8	12	16	24	32	
Visit Window ^b (days relative to nominal visit)	-2		±2	±2	±2	±2	±2	±5	
Efficacy Assessments (eDiary and ePROs^{g,h})									
eDiary recording ⁱ	✓	✓ ^j	✓	✓	✓ ^j	✓	✓ ^k		✓ ^k
eDiary compliance check ^l		✓	✓	✓	✓	✓	✓		
PGIC			✓		✓ ^j	✓	✓		✓
MBS	✓	✓ ^j			✓ ^j		✓		✓
HADS		✓ ^j	✓		✓ ^j		✓		✓
Digital device (optional) ^m	✓	✓	✓	✓	✓ ⁿ				✓ ⁿ
Pharmacoeconomic Assessments (ePROs^{g,h})									
HIT-6		✓ ^j	✓		✓ ^j		✓		✓
mMIDAS		✓	✓		✓		✓		✓
MSQ v2.1		✓ ^j	✓		✓ ^j		✓		✓
EQ-5D-5L		✓ ^j	✓		✓ ^j		✓		✓
HCRU		✓ ^j	✓		✓ ^j		✓		✓
WPAI:M		✓ ^j	✓		✓ ^j		✓		✓
TSQM-9		✓ ^j	✓		✓ ^j		✓		✓
Safety Assessments									
Adverse events			✓ ^{o,p,q}	✓	✓	✓ ^{o,p,q}	✓	✓	✓
Vital signs (including body temperature)	✓	✓ ^{p,q}			✓ ^{p,q}		✓		✓

Visit Name	Screening	Placebo-controlled Period		Open-label Period		Safety Follow-up Decentralized	Withdrawal
		Baseline + IMP	PO Visit, Decentralized ^c	Decentralized ^c	IMP		
Visit Number	1	2	3	4	5	6	7
End of Week ^a	-4	0	4	8	12	16	24
Visit Window ^b (days relative to nominal visit)	-2		±2	±2	±2	±2	±5
Other Trial Procedures and Assessments							
Brief educational intervention ^r , including SDS:H SDS:H		✓			✓		
IMP administered (intravenous infusion) ^s		✓ ^{o,t}			✓ ^{o,t}		
IMP accountability ^u		✓		✓	✓		
Concomitant medication (prescription and non-prescription: traditional herbal medicines, non-pharmacological interventions, vitamins, and mineral supplements)		✓ ^q	✓	✓	✓ ^q	✓	✓
Substance use (alcohol, tobacco, caffeine, marijuana)		✓	✓	✓	✓		✓ ^v
eDiary training ^h		✓					
ePRO training ^h		✓					
eDiary closeout ^k						✓	✓
Pregnancy test ^w		✓	✓		✓	✓	✓

β-HCG = human chorionic gonadotropin; C-SSRS = Columbia-Suicide Severity Rating Scale; ECG = electrocardiogram; EoT = end of trial; eDiary = electronic diary; ePRO = electronic patient-reported outcome; EQ-5D-5L = Euroqol 5 Dimensions; FSH = follicle-stimulating hormone; HADS = Hospital Anxiety and Depression Scale; HCRU = Health Care Resource Utilization; HIT-6 = Headache Impact Test; IMP = investigational medicinal product; MBS = Most Bothersome Symptom; mMIDAS = modified Migraine Disability Assessment; MOH = medication overuse headache; MSQ v2.1 = Migraine-Specific Quality of Life Questionnaire Version 2.1; PGIC = Patient Global Impression of Change; PO = primary outcome; SDS:H = Severity of Dependence Scale Adapted for Headache; TSQM-9 = Treatment Satisfaction Questionnaire for Medicine – 9 items; WD = withdrawal; WPAI:M = Work Productivity and Activity Impairment questionnaire, Migraine version

- All assessments may be completed over a maximum of 2 consecutive days with the exception of ePROs (see footnote g below); if so, the first day is considered the “visit” day according to the schedule.
- If the date of an on-site visit or decentralized contact does not conform to the schedule, subsequent visits should be planned to maintain the visit schedule relative to the Baseline Visit. In exceptional cases, the screening period (visit interval between Screening and Baseline Visits) may be extended by an extra period of seven days with approval from the

sponsor (the medical expert at H. Lundbeck A/S or the CRO's medical monitor) based on the provided rationale.

- c. For decentralized visits, the participant will be contacted for eDiary compliance check, to ensure that the selected assessments have been completed and for collection of relevant information such as adverse events and concomitant medications.
- d. Participants who withdraw their consent for trial participation should be withdrawn from the study. However, all efforts should be done to keep the participants who interrupted/terminated their IMP infusion in the trial and all assessments should be performed as described in the protocol. If participants want to withdraw from the study and thus not willing to attend the remaining visits as scheduled, they will be asked to attend a Withdrawal Visit as soon as possible and a further Safety Follow-up Visit at 20 weeks after administration of IMP.
- e. Participants' available adequately documented records of migraine and MOH history and previous migraine preventive medication use (including treatment failures) within the 5 years prior to the Screening Visit.
- f. The C-SSRS at Screening Visit will be administered by the authorized rater at the clinical site.
- g. ePROs scheduled at Baseline Visit (Visit 2) and Week 12 Visit (Visit 5) must be completed in the clinical site on the visit date and before the infusion. ePROs which are scheduled in alignment with the Withdrawal Visit can be completed in the clinical site or in a remote setting within 3 days prior to the scheduled on-site visit date. ePROs which are scheduled in alignment with a decentralized contact must be completed in a remote setting and can be completed on the day or within 3 days prior to the scheduled decentralized contact date.
- h. At the Screening Visit, the participant must be assisted with the provisioning and training of the eDiary and ePROs. Details will be provided in a separate user manual.
- i. The eDiary assessments will be completed in the remote setting on a daily basis from Screening to EoT.
- j. On the Baseline Visit and Week 12 Visit day, participants must complete the ePRO entries prior to infusion. Participants must ensure to complete eDiary recording of headaches that ended prior to infusion (that is, for headaches which are ongoing or not yet recorded in the eDiary). For TSQM-9, due to no exposure of IMP prior to Baseline Visit, the assessment of overall IMP satisfaction with the TSQM-9 at Baseline visit will be used only as practice.
- k. The eDiary closeout will take place at EoT Visit/Withdrawal Visit while the participant is at the clinical site. Details will be provided in a separate user manual.
- l. In addition to the eDiary compliance checks performed at the defined on-site visits and decentralized contacts, ongoing evaluation of eDiary compliance will be performed by the site (based on eDiary reporting) and more frequent contact with participants may be needed in case of non-compliance.
- m. At designated sites, the participants undergoing the additional actigraphy assessments must provide a signed digital device Informed Consent Form.
- n. Hand in of Digital device. Participants undergoing the additional actigraphy assessments who drop out from the trial before Visit 5 must hand in the device at the Withdrawal Visit.
- o. Infusion Related Reactions must be checked as part of the overall adverse event collection, during/after infusion and before the participant is discharged from the site.
- p. Infusion must be preceded by the assessment of vital signs including body temperature, concomitant medications, and adverse events.

- q. Vital signs including body temperature and adverse events must be checked after infusion.
- r. The brief educational intervention must take place prior to IMP infusion.
- s. An unblinded pharmacist or designee is responsible for receiving, storing and preparing IMP. The pharmacist or designee will not be responsible for other aspects of the clinical trial where blinding is necessary.
- t. Participants must be monitored during and after the infusion in accordance with usual clinical practice.
- u. A designated unblinded clinical research associate (CRA) is responsible for the IMP accountability.
- v. Substance use will only be collected if the patient withdraws during the Placebo-controlled Period.
- w. For women of childbearing potential, pregnancy test at the Screening Visit is to be conducted using serum β -HCG. At all other visits, where this is applicable the urine pregnancy testing will be performed using a urine stick test and in case of a positive finding, further confirmatory testing will be performed via serum β - human chorionic gonadotropin (β -HCG).

